ATTACHMENT

Attachment 1: Analytical considerations on joints with joint procedure/injection prior to study ^a

Procedures/Injection	Impact on Joint Count Outcome
Synovectomy	Not evaluable
Arthrodesis	Not evaluable
Joint replacement	Not evaluable
Amputation	Not evaluable
Arthrocentesis	Evaluable if happened > 3 months prior to baseline
Excision / Resection	Not evaluable
Arthrotomy	Not evaluable
Arthroscopy – surgical	Evaluable if happened > 3 months prior to baseline
	visit, otherwise not evaluable
Arthroscopy – diagnostic	Evaluable if happened > 4 weeks prior to baseline
	visit, otherwise not evaluable
Chondroplasty	Evaluable if happened > 4 weeks prior to baseline
	visit, otherwise not evaluable
Synovial cyst aspiration	Evaluable if happened > 4 weeks prior to baseline
	visit, otherwise not evaluable
Needle biopsy – synovium	Evaluable if happened > 3 months prior to baseline
	visit, otherwise not evaluable
Osteotomy	Not evaluable
Radio synovectomy	Not evaluable
Tendon surgery	Not evaluable
Bursal surgery	Not evaluable
Fracture reduction	Not evaluable
Steroid injection (IA, tendon,	Evaluable if happened > 3 months prior to baseline
sheath, bursa)	visit, otherwise not evaluable
Other injection	Not evaluable
a The joint assessors may mark a	a joint as not evaluable based on his clinical judgment, which is not

^a The joint assessors may mark a joint as not evaluable based on his clinical judgment, which is not included in this table.

Attachment 2: Analytical considerations on joints with injection and/or joint surgery for reasons NOT related to JIA during the study ^a

Procedures/Injection	Impact on Joint Count Outcome
Synovectomy	Not evaluable from procedure date onward
Arthrodesis	Not evaluable from procedure date onward
Joint replacement	Not evaluable from procedure date onward
Amputation	Not evaluable from procedure date onward
Arthrocentesis	Not evaluable from procedure date onward
Excision / Resection	Not evaluable from procedure date onward
Arthrotomy	Not evaluable from procedure date onward
Arthroscopy – surgical	Evaluable if happened > 3 months prior to evaluation, otherwise not evaluable
Arthroscopy – diagnostic	Evaluable if happened > 4 weeks prior to evaluation, otherwise not evaluable
Chondroplasty	Evaluable if happened > 4 weeks prior to evaluation, otherwise not evaluable
Synovial cyst aspiration	Evaluable if happened > 4 weeks prior to evaluation, otherwise not evaluable
Needle biopsy – synovium	Evaluable if happened > 3 months prior to evaluation, otherwise not evaluable
Osteotomy	Not evaluable from procedure date onward
Radio synovectomy	Not evaluable from procedure date onward
Tendon surgery	Not evaluable from procedure date onward
Bursal surgery	Not evaluable from procedure date onward
Fracture reduction	Not evaluable from procedure date onward
Steroid injection (IA, tendon, sheath, bursa)	Evaluable if happened > 3 months prior to evaluation, otherwise not evaluable
Other injection	Not evaluable from procedure date onward
-	joint as not evaluable based on his clinical judgment, which is not

included in this table.

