While it may be reasonable in clinical practice to identify as "nonevaluable" any joint which in the past or during study participation has been surgically altered (ie, prosthesis placement) or

medically treated (ie, intra-articular injection), the designation of "nonevaluable" for the purposes of this study is slightly different. Joints should only be designated as "nonevaluable" by the consistent joint assessor in the ePRO device if it is physically impossible to assess the joint (ie, joint inaccessible due to a cast, joint not present due to an amputation, joint deformed so as to make it impossible to assess).

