5.1.3. Joint Evaluability

For subjects who have a joint injection or surgical procedure prior to the date of enrollment, the affected joints will be analyzed according to the impact of the joint injection or joint surgical procedure on the evaluability of the involved joints. See Attachment 1 for details. If a joint is considered nonevaluable at baseline, then all post-baseline joint evaluations will also be considered as nonevaluable; furthermore, this nonevaluability overrides any other documented, post baseline joint assessments. For subjects undergoing joint injections and/or procedures during the study for reasons not related to JIA, joint evaluability is summarized in Attachment 2.

For subjects undergoing a joint procedure/injection for the treatment of JIA, the corresponding joint(s) will be counted as swollen, having active arthritis, and having limited range of motion from the date of procedure onward.

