5.1.4. Adjusted Joint Counts Rules

For subjects who have an incomplete set of evaluable joints, the joint count will be adjusted to a 69 joint count for joints with limited range of motion and 73 joint count for active joints for JIA ACR endpoints. This is done by dividing the number of affected joints by the number of evaluable joints and multiplying by 69 and 73, respectively.

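### SAP Attachment 2 permanently excludes a joint aspirated during the study for a non-JIA reason, unlike its own 3-month rows and unlike Attachment 1, and this can make the active-joint count look improved

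*SAP*

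**What the plan says.** SAP 5.1.3 sends procedures before enrolment to Attachment 1, and procedures during the study for reasons unrelated to JIA to Attachment 2. The two tables list the same 19 procedures.

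- Attachment 2 (during the study, not for JIA): "Arthrocentesis Not evaluable from procedure date onward".
- Attachment 1 (before the study): "Arthrocentesis Evaluable if happened > 3 months prior to baseline".
- Attachment 2, for surgical arthroscopy, synovial needle biopsy and steroid injection: "Evaluable if happened > 3 months prior to evaluation, otherwise not evaluable". Diagnostic arthroscopy, chondroplasty and synovial cyst aspiration return after 4 weeks.

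Procedures done to treat JIA follow another rule in SAP 5.1.3: "the corresponding joint(s) will be counted as swollen, having active arthritis, and having limited range of motion from the date of procedure onward".

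When some joints are not evaluable, SAP 5.1.4 rescales the count for the JIA ACR endpoints, to 69 joints for limited motion and 73 for active joints: "This is done by dividing the number of affected joints by the number of evaluable joints and multiplying by 69 and 73, respectively". It does not say whether the baseline count is recomputed on the joints that remain evaluable later. Under SAP 5.4.1.1, a fall in a component counts as improvement.

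**The concern.** Attachment 2 treats a needle aspiration more severely than surgery through an arthroscope or a needle biopsy of the same joint, and it gives no reason. One mismatch in 19 otherwise parallel rows looks like a table error, although the documents cannot show intent.

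The direction matters. The joint is in the baseline count and leaves the later counts. If it still has active arthritis, its removal reads as improvement. Under the arthrocentesis row this lasts through Week 52, the final efficacy assessment named in protocol 9.2.1.1. Under the neighbouring rows it would last about 3 months. The active-joint count feeds the JIA ACR responses, and having no active joints is one criterion of inactive disease (SAP 5.4.1.2). JIA ACR 30 at Week 28 also drives the rule to discontinue the study if fewer than 50% respond (protocol 3.1.1, SAP 1.2).

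**Working it through.** **Row comparison.** Of the 19 procedures in Attachment 2, 13 are permanent (arthrocentesis and 12 others), 3 carry a 3-month limit and 3 a 4-week limit: 13 + 3 + 3 = 19. Set against Attachment 1, 18 rows have the same rule and one, arthrocentesis, differs.

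**Inputs.** At least 5 active joints at entry (protocol 4.1, criterion 5); multiplier 73 for active joints (SAP 5.1.4); 30% threshold per component (SAP 5.4.1.1). The plan gives no figure of its own on this point to reproduce.

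**Formula.** Adjusted count = active ÷ evaluable × 73. With *a* active joints and all 73 evaluable, the count is *a*. If one active joint becomes non-evaluable, the count is (*a* − 1) ÷ 72 × 73. The fall is *a* − (*a* − 1) × 73/72 = (73 − *a*)/72, which is positive for every *a* below 73. The rescaling therefore gives back only (*a* − 1)/72 of a joint.

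**Results**, with one active joint dropped and the baseline count left as recorded:

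| Active at baseline | Truly active now | Computed count now | True improvement | Computed improvement |
|---|---|---|---|---|
| 5 | 5 | 4/72 × 73 = 4.06 | 0% | 18.9% |
| 6 | 6 | 5/72 × 73 = 5.07 | 0% | 15.5% |
| 10 | 10 | 9/72 × 73 = 9.13 | 0% | 8.8% |
| 20 | 20 | 19/72 × 73 = 19.26 | 0% | 3.7% |
| 5 | 4 | 3/72 × 73 = 3.04 | 20.0% | 39.2% |
| 6 | 5 | 4/72 × 73 = 4.06 | 16.7% | 32.4% |
| 7 | 6 | 5/72 × 73 = 5.07 | 14.3% | 27.6% |
| 12 | 9 | 8/72 × 73 = 8.11 | 25.0% | 32.4% |

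With no true change, one dropped joint never reaches 30% in an eligible child. It matters for children near the threshold.

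**Other cases.**
- If the joint also has limited motion, a second component moves: 4/68 × 69 = 4.06 from 5, a fall of 18.8%.
- If the dropped joint is the last active one, the count is 0/72 × 73 = 0. The joint criterion of inactive disease is then met, provided non-evaluable joints are simply ignored there; the SAP gives no rule.
- If the dropped joint is inactive, the count rises slightly: 5/72 × 73 = 5.07 from 5.

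**The baseline assumption.** If the baseline were recomputed on the 72 remaining joints, the unchanged child would go from 4.06 to 4.06 (0%). The child with 5 then 4 active joints would go from 4.06 to 3.04, which is (4 − 3)/4 = 25%, below 30%. The size of the effect depends on a rule that SAP 5.1.4 does not state.

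**With a 3-month rule.** Once 3 months have passed, the unchanged child counts 5/73 × 73 = 5.00, a change of 0%.

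**The case against.** Several points on the other side stand.

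- **Scope.** The row covers only aspirations unrelated to JIA. An aspiration to treat JIA makes the joint count as active from then on, which is the conservative direction. The problem needs a joint with active arthritis that is aspirated for some other reason. The documents give no frequency, and it is probably low.
- **Limited reach.** The active-joint count is one of six JIA ACR components, and a response needs three. Inactive disease also requires normal CRP, a low physician global score, short morning stiffness, no active uveitis and no systemic features. A reader might infer that an affected child would be scored as a responder or as having inactive disease. The documents support only that one component or one criterion could be met wrongly.
- **Not unique to this row.** Twelve other Attachment 2 rows are permanent and act on the count in the same way. A 3-month rule also leaves the effect in place for those 3 months (about 13 weeks): at Week 28, an aspiration after about Week 15 is excluded under either wording.
- **Which row is wrong.** The Attachment 1 row lacks the ending that the other time-limited rows carry, so it may be the incomplete one, or it may have been cut in extraction. The neighbouring rows make a 3-month rule plausible but do not prove it.

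Two stronger readings are tempting and fail. The first is that Attachment 1 restores an aspirated joint after 3 months. It does not: it looks back once from baseline, and SAP 5.1.3 then says "If a joint is considered nonevaluable at baseline, then all post-baseline joint evaluations will also be considered as nonevaluable". If exclusion is implied for recent aspirations, a joint aspirated 2 months before baseline is also lost for the whole study. The like-for-like comparison is with the other 3-month rows of Attachment 2. The second is that the protocol keeps this joint evaluable. Protocol 9.2.1.1 restricts the non-evaluable label to use "by the consistent joint assessor in the ePRO device if it is physically impossible to assess the joint". That governs the assessor's entry, and it sits equally badly with every procedure-based exclusion in both attachments, including the 3-month rows used here as the model.

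**Conclusion.** The inconsistency is real, and nothing elsewhere in the documents explains it. For an affected child whose aspirated joint is still active, the stated rule biases the active-joint component towards improvement: by 18.9% at 5 active joints and 8.8% at 10, with no clinical change. It can carry a near-threshold child past 30% on that component (20% true, 39.2% computed). This rests on two assumptions: that the joint has active arthritis when it drops out, and that the baseline count is not recomputed.

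The consequence for the trial is small. Efficacy is descriptive, with no testing and no primary or major secondary efficacy endpoint, and the primary PK endpoint is unaffected. For the 50% discontinuation rule, one child wrongly classed as a responder among about 120 moves the rate by 1/120, or 0.8 percentage points. This is a tidy-up of the SAP and does not threaten its conclusions.

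**What to change.** In SAP Attachment 2, give arthrocentesis the wording of the table's other 3-month rows: "Evaluable if happened > 3 months prior to evaluation, otherwise not evaluable". In Attachment 1, complete the arthrocentesis row so that it says what happens to a joint aspirated within 3 months of baseline, as the other time-limited rows do. If permanent exclusion is intended, state the reason and make the two attachments agree.

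A sentence in SAP 5.1.4 saying whether the baseline count is recomputed on the joints still evaluable would also settle the same question for the other permanent rows.

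The cost is one or two table cells, plus that sentence if it is added. No new data are needed, because under protocol 9.2.1.1 treatment of a joint is not in itself a reason to stop assessing it. The remaining downside is that the joint stays excluded for the first 3 months.

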Attachment 3: Markedly Abnormal Laboratory Parameter Criteria

Table 3 Markedly abnormal criteria for laboratory parameters			
Hematology Test	Criteria for Markedly Abnormal Status		
Hemoglobin (g/L)	Decrease > 20.0 AND Value < 100.0		
Hematocrit (%)	Value < 0.27		
Total WBC (x10 ⁹ /L)	Value < 2.0 OR Value > 20.0		
Neutrophils, absolute (x10 ⁹ /L)	Percent decrease ≥33 AND Value < 1.5		
Lymphocytes, absolute (x10 ⁹ /L)	Percent decrease ≥ 33 AND Value < 1.5		
Eosinophils, absolute (x10 ⁹ /L)	Percent increase ≥ 100 AND Value > 1.3		
Platelet count (x10 ⁹ /L)	Percent decrease ≥50 AND Value < 75		
Chemistry Test	Criteria for Markedly Abnormal Status		
Alkaline phosphatase (U/L)	Percent increase ≥ 100 AND Value > 500		
ALT (U/L)	Percent increase ≥100 AND Value > 150		
AST (U/L)	Percent increase ≥ 100 AND Value > 150		
Total bilirubin (umol/L)	Percent increase ≥ 100 AND Value > 51.3		
Sodium (mmol/L)	(Increase ≥10 AND Value > 150) OR (Decrease ≥ 10 AND Value < 120)		
Potassium (mmol/L)	(Increase ≥ 0.8 AND Value > 5.5) OR (Decrease ≥ 0.8 AND Value < 3.0)		
Chloride (mmol/L)	Value < 85 OR Value > 120		
BUN/Urea (mmol/L)	Percent increase ≥ 66 AND Value > 14.28		
Creatinine (umol/L)	Percent increase ≥ 66 AND Value > 132.6		
Albumin (g/L)	Decrease ≥ 10.0 AND Value < 30.0		
Total protein (g/L)	Value < 45 OR Value > 100		
Calcium (mmol/L)	(Increase ≥ 0.37 AND Value > 2.62) OR (Decrease ≥ 0.37 AND Value < 1.87)

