• Of childbearing potential, and if sexually active, practicing a highly effective method of birth control consistent with local regulations regarding the use of birth control methods for subjects participating in clinical studies: eg, established use of oral, injected or implanted hormonal methods of contraception; placement of an intrauterine device (IUD) or intrauterine system (IUS); barrier methods: condom with spermicidal foam/gel/film/cream/suppository or occlusive cap (diaphragm or cervical/vault caps) with spermicidal foam/gel/film/cream/suppository; male partner sterilization (the vasectomized partner should be the sole partner for that subject); true abstinence (when this is in line with the preferred and usual lifestyle of the subject and at the discretion of the investigator/per local regulations). Girls of

childbearing potential must agree not to donate eggs (ova, oocytes) for the purposes of assisted reproduction during the study and for 6 months after receiving the last dose of study drug.

Note: If the childbearing potential changes after start of the study (eg, girl who is not heterosexually active becomes active, premenarchal girl experiences menarche) a girl must begin a highly effective method of birth control, as described above.

- 13. Girls of childbearing potential must have a negative serum β -human chorionic gonadotropin (β -hCG) test at screening and a negative urine pregnancy test at each study visit where golimumab infusion is to take place.
- 14. Boys must practice abstinence, or if sexually active with a girl of childbearing potential and has not had a vasectomy must agree to use a barrier method of birth control eg, either condom with spermicidal foam/gel/film/cream/suppository or partner with occlusive cap (diaphragm or cervical/vault caps) with spermicidal foam/gel/film/cream/suppository, and all boys must also not donate sperm during the study and for 6 months after receiving the last dose of study drug.
- 15. Subjects' screening laboratory tests must meet the following criteria:
 - a. Hemoglobin: ≥8.0 g/dL (SI: ≥80 g/L; girls and boys, ages 2 to 11)
 ≥8.5 g/dL (SI: ≥85 g/L; girls, ages 12 to 18)
 ≥9.0 g/dL (SI: ≥90 g/L; boys, ages 12 to 18)
 - b. White blood cells (WBCs) $\geq 3.0 \times 10^3 \text{ cells/}\mu\text{L}$ (SI: $\geq 3.0 \times 10^9 \text{ cells/}\text{L}$)
 - c. Neutrophils $\ge 1.5 \text{ x } 10^3 \text{ cells/}\mu\text{L (SI: } \ge 1.5 \text{ x } 10^9 \text{ cells/}\text{L)}$

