4.1. Demographics and Baseline Characteristics

The baseline measurement is defined as the closest measurement taken prior to the first study agent administration (Week 0) unless otherwise stated.

Subjects' demographic data including age, race, gender, height, weight, BSA, and BMI at baseline will be summarized. Baseline disease characteristics including duration of disease and baseline JIA efficacy assessments will be summarized.

Baseline TB information and medication usage will also be summarized.

The number of subjects will also be summarized by geographic region, country, and investigational site.

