6.3. Clinical Laboratory Tests

The laboratory parameters include but are not limited to the following:

Hematology: hemoglobin, hematocrit, neutrophils, lymphocytes, monocytes, eosinophils, platelets, and WBC count.

Chemistry: BUN/urea, creatinine, total bilirubin, alkaline phosphatase, ALT/SGPT, AST/SGOT, bicarbonate, sodium, potassium, calcium, albumin, chloride, phosphate, glucose, uric acid and total protein.

Laboratory results will be graded according to NCI-CTCAE version 4.03 or later. Note that toxicity grading for creatinine increase will be based on the NCI CTC v4.03 or later criteria, but limited only to the part based on the upper limit of normal (ULN), the other part, that is based on change from baseline, will not be used for toxicity grading. Generic normal ranges will be applied whenever reference ranges are not available.

17

NCI-CTCAE grades will be used in the summary of laboratory data (Grade 0-4). The proportion of subjects for select laboratory parameters with maximum Grades will be presented. In addition, the proportion of subjects with markedly abnormal laboratory results will also be provided. The subjects' maximum post-baseline ALT and AST will also be summarized by TB prophylaxis (TB prophylaxis, or no TB prophylaxis).

Levels of laboratory values that are considered to be markedly abnormal have been defined for each laboratory parameter in Attachment 3.

Boxplots will be used to describe the selected laboratory analyte at baseline and at each scheduled time point. The selected laboratory analytes are: WBC counts, neutrophils, hemoglobin, platelets, ALT, and AST.

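### SAP Attachment 3 sets the markedly abnormal hematocrit limit at 0.27 in a row labelled percent, so on percent data the row can never be met

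*SAP*

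**What the plan says.** SAP Attachment 3 has two red-cell rows. Hemoglobin, in g/L, is markedly abnormal when "Decrease > 20.0 AND Value < 100.0"; both parts are required. Hematocrit is labelled in percent and is markedly abnormal below 0.27, with no condition on change. Attachment 3 does not say what the decrease is measured from. SAP 4.1 supplies the natural reading: "The baseline measurement is defined as the closest measurement taken prior to the first study agent administration (Week 0" visit).

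Protocol 4.1, criterion 15a, sets the hemoglobin floors at screening: "≥80 g/L; girls and boys, ages 2 to 11"; "≥85 g/L; girls, ages 12 to 18"; "≥90 g/L; boys, ages 12 to 18".

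These criteria feed two outputs: the proportion of subjects with markedly abnormal results (SAP 6.3) and a listing of those subjects (Protocol 11.7).

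Other laboratory summaries are planned. SAP 6.3 states that "NCI-CTCAE grades will be used in the summary of laboratory data (Grade 0-4"), and that "The proportion of subjects for select laboratory parameters with maximum Grades will be presented", without naming the parameters. It also plans boxplots at baseline and each scheduled time point: "The selected laboratory analytes are: WBC counts, neutrophils, hemoglobin, platelets, ALT, and AST". Protocol 11.7 adds cross-tabulations of results before and after treatment against normal ranges, and frequency tabulations of abnormalities.

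**The concern.** The hematocrit label and limit cannot both be right. If the database holds hematocrit in percent and the rule is programmed literally, the row returns no cases. A reader of the study report would take that for a clean result.

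The row also has a particular job. Hemoglobin pairs a level with a fall from baseline, so for a child who starts low the fall decides whether the flag is raised. Hematocrit carries no such condition, which makes it the only red-cell criterion in the table that can flag a low absolute value whatever the starting point. If it does not work, a child who enters with low hemoglobin and falls further by up to 20 g/L appears in neither the markedly abnormal proportion nor the listing.

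**Working it through.** The plan gives no derived figure to reproduce. The check applies the two rules as written.

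**Hematocrit.** Rule: flag if the value is below 0.27.

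- Values recorded in percent: 15, 18, 20, 24 and 26.9 all exceed 0.27, so none is flagged.
- The same values as fractions (0.15, 0.18, 0.20, 0.24, 0.269): all are flagged; 0.27 and 0.30 are not.
- Scale check, assuming 310 to 350 g of hemoglobin per litre of red cells (not in the documents): a hematocrit of 0.27% would mean hemoglobin of 0.0027 × 310 = 0.84 to 0.0027 × 350 = 0.95 g/L. No realistic percent value meets the row.

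**Hemoglobin.** Rule: flag if (baseline − value) > 20 and value < 100. The flag point is therefore min(baseline − 20, 100).

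| Baseline (g/L) | Flagged only below (g/L) | Fall at that point |
|---|---|---|
| 80 (floor, ages 2 to 11) | 60 | 20 (25.0%) |
| 85 (floor, girls 12 to 18) | 65 | 20 (23.5%) |
| 90 (floor, boys 12 to 18) | 70 | 20 (22.2%) |
| 100 | 80 | 20 (20.0%) |
| 110 | 90 | 20 (18.2%) |
| 120 | 100 | 20 (16.7%) |
| 140 | 100 | 40 (28.6%) |

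Below a baseline of 120 g/L the 100 g/L level never decides the outcome. A child going from 82 to 65 g/L has fallen 82 − 65 = 17 and is not flagged; a child going from 121 to 99 g/L has fallen 121 − 99 = 22 and is flagged.

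**The two rows together.** With the same 310 to 350 g/L assumption:

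- A hematocrit of 27% corresponds to hemoglobin of 0.27 × 310 = 83.7 to 0.27 × 350 = 94.5 g/L.
- Hemoglobin of 65 g/L corresponds to a hematocrit of 65/350 = 0.186 to 65/310 = 0.210, so the child falling from 82 to 65 g/L is caught if the row works as a fraction.
- Hemoglobin of 60 to 70 g/L corresponds to 60/350 = 0.171 up to 70/310 = 0.226, so the unflagged values at the three hemoglobin limits are also caught.
- A child who enters at 80 g/L and does not change (80/350 = 0.229 to 80/310 = 0.258) would be flagged too, because the row ignores baseline.

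A working hematocrit row therefore closes the gap at the entry floors; a row that never fires leaves it open.

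**The case against.** The best reply is that this is a label slip. Hemoglobin is in g/L, cell counts are per litre and most chemistry rows are in SI units, so 0.27 reads naturally as a fraction. On that reading the row works and catches the cases that the hemoglobin row misses. This is probably the intent. What stands against it is that the row is an analysis rule and not background text, and nothing in the documents fixes the stored unit.

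A reader might infer that the hemoglobin rule is itself defective and should gain an alternative tied to the entry floors. The documents do not support that. Pairing a change with a level is the table's design for most analytes, including neutrophils, platelets, ALT, AST, creatinine and albumin; it separates change on study from status at entry. Nor does the rule bear only on low starters: from 140 g/L the fall must exceed 40 g/L. An entry-floor rule would call a move from 80 to 79 g/L markedly abnormal.

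A reader might also infer that the safety analysis as a whole understates anemia. That goes too far. Laboratory results are graded by CTCAE, hemoglobin is plotted by visit, Protocol 11.7 plans shift tables, and Protocol 9.4 has investigators record clinically relevant laboratory changes as adverse events.

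These do not fully replace the flag. The graded parameters are not named, and the six named analytes belong to the boxplots. Boxplots do not give the proportion affected. A child already below the normal range who falls further shows no shift (the range is not given, so 82 g/L being below it is an assumption).

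**Conclusion.** The hematocrit row is wrong as written and should be corrected; the matter is minor. If the data are in percent and the rule is applied literally, the count is zero whatever the data. If the data are fractions, the result is right and only the label is wrong. The documents do not settle which applies.

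The consequence is confined to the markedly abnormal table and listing. There, without a working hematocrit row, a child with a baseline of 80, 85 or 90 g/L is not flagged until below 60, 65 or 70 g/L. How many children this concerns is unknown, because no baseline hemoglobin distribution is given; it may be none. No hypothesis is tested and no primary endpoint is involved.

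The conclusion assumes that the decrease is taken from the SAP 4.1 baseline. The entry floors apply at screening, so a child's baseline may differ if a Week 0 sample is used. The statement that a working hematocrit row covers the gap rests on the assumed hemoglobin-to-hematocrit ratio.

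**What to change.** In SAP Attachment 3, state the hematocrit limit as below 27 if the database holds percent, or relabel the row as a fraction (L/L) and keep 0.27. Check the stored unit before programming.

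In SAP 6.3, name hemoglobin among the parameters in the CTCAE maximum-grade table, so that low absolute values are reported whatever the baseline. This assumes that the hemoglobin grades are set on absolute level; the SAP does not reproduce them.

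It would also help to say in Attachment 3 that a decrease is measured from baseline. The hemoglobin criterion can stay as it is.

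The cost is a few words of SAP text and no new data collection. If hematocrit would otherwise have been programmed literally on percent data, the flagged proportion may rise, and it may include children who entered with low values and did not change.
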